6.2 Secondary Objectives

- To assess annualized HV in children with GHD at 26 weeks of weekly TransCon hGH treatment
- To assess the proportion of subjects with IGF-1 SDS in the normal range of 0.0 to +2.0 at 26 weeks of weekly TransCon hGH treatment
- To evaluate Δ HSDS in children with GHD at 26 weeks of weekly TransCon hGH treatment
- To determine the incidence of antibodies against TransCon hGH (anti-hGH and anti-PEG) in children with GHD over 26 weeks of weekly TransCon hGH treatment
- To assess the expected C_{\max} of TransCon hGH in children with GHD ≥ 6 months to < 3 years old
- To assess the preference for weekly TransCon hGH or commercially available daily hGH treatment
- To assess the treatment satisfaction of weekly TransCon hGH over time

7. TRIAL DESIGN

7.1 Overall Trial Design and Plan

7.1.1 Trial Design

This is a multicenter phase 3, open-label, 26-week trial of weekly TransCon hGH in children 6 months to 17 years old, inclusive, with GHD. Children ≥ 6 months but < 3 years old with GHD may be hGH-treatment naïve or have been treated with daily hGH (≥ 0.20 mg hGH/kg/week) for ≤ 130 weeks. Children 3 to 17 years old, inclusive, must have been treated with daily hGH (≥ 0.20 mg hGH/kg/week) for ≥ 13 weeks but ≤ 130 weeks and be without evidence of closed epiphyses.

The trial will be conducted at up to approximately 50 sites specialized in the management of pediatric GHD.

The trial consists of:

- 1) Screening Period – up to approximately 4 weeks
- 2) Treatment Period – up to 27 weeks of dosing

The total duration of participation for each subject in the trial will therefore be up to approximately 31 weeks (Figure 3).

Each subject who successfully completes the trial on study drug will be invited to participate in the CT-301EXT (extension) Trial designed to assess long-term safety and efficacy.

Figure 3
Overall Trial Design

7.1.2 Measures Taken to Minimize Bias

A subject's visits should be performed at approximately the same time of day. Also, assessments should be performed in a similar fashion at each visit. Subjects' height in particular will preferably be measured by the same auxologist and either with the subject always barefoot or in thin foot covers.

Additionally, all efforts will be made to keep missing data to a minimum, including the following:

- Investigators will be trained about the importance of subject retention
- Investigators will be instructed to encourage subjects to complete all trial visits, including any subjects who discontinue the study drug early
- The Informed Consent Form (ICF) and Assent Form will include a statement educating subjects and parents/legal guardians about the scientific importance of their data even if the subject discontinues study drug early
- Special efforts will be made to provide assistance to subjects/families who might discontinue due to travel or cost barriers, such as offers of transportation to the clinic
- C_{\max} Visit, Visit 2, and Visit 3 have visit windows to allow flexibility for clinic attendance (see [Section 10.2.2](#))
- Fasting is not required to improve attendance at all study visits
- Every effort will be made to contact subjects/parents/legal guardians or other family members to maintain contact with the clinic

7.2 Trial Sites

The trial will be conducted at up to approximately 50 sites. All centers will be specialized treatment centers in the management of pediatric GHD.

7.3 Termination Rules

7.3.1 Early Termination of Subjects

Valid reasons for which a subject's participation in the clinical trial may be discontinued include the following:

- Withdrawal of consent by the subject or parent/legal guardian
- Subject is lost-to-follow-up

For procedures to be performed for subjects discontinuing study drug and/or trial participation, refer to [Section 8.2](#).

7.3.2 Early Termination of the Trial

The Sponsor reserves the right to discontinue or suspend the trial at any time in the event of any of the following:

- Inefficacy of the study drug

- Occurrence of AEs unknown to date with respect to their nature, severity, and duration, or an unexpected incidence of known AEs such that the Sponsor has determined that continued treatment with TransCon hGH presents an unreasonable and significant risk of illness or injury
- Medical or ethical reasons affecting the continued performance of the trial
- Difficulties in the recruitment of subjects
- Cancellation of drug development

The Sponsor may stop this trial at a particular site for any of the following reasons:

- The site cannot include an adequate number of subjects
- Serious and/or persistent non-compliance with the protocol or clinical trial conduct
- Careless or premeditated false documentation in the electronic case report form (eCRF)
- Inadequate cooperation with the investigator
- Non-compliance with GCP and/or regulatory requirements
- The investigator requests discontinuation

8. SUBJECT POPULATION

Approximately 150 male and female children who at Visit 1 are 3 to 17 years old, inclusive, diagnosed with GHD, weigh no more than 80 kg, have open epiphyses, and have received at least 0.20 mg hGH/kg/week of daily hGH treatment for ≥ 13 weeks but ≤ 130 weeks may enter this trial.

Additionally, children with GHD who at Visit 1 are ≥ 6 months but < 3 years old, weigh at least 5.5 kg, and are either hGH treatment-naïve or have received at least 0.20 mg hGH/kg/week of daily hGH treatment for ≤ 130 weeks may enter this trial.

8.1 Trial Entry Criteria

8.1.1 Inclusion Criteria

- 1) Investigator-determined GHD diagnosis together with at least one of the following prior to the historical initiation of daily hGH therapy:
 - a. 2 GH stimulation test(s) with peak GH level of ≤ 10 ng/mL
 - b. Impaired height defined as at least one of the following:
 - i) ≥ 2 SD below the mean height for chronological age and sex when compared to the relevant growth charts:
 - (1) 2006 WHO Child Growth Standards for < 2 years old

- (2) 2000 CDC Growth Charts for the United States for ≥ 2 years old
 - ii) ≥ 1.5 SDS below mid-parental height
 - c. IGF-1 level ≥ 1 SD below the mean IGF-1 level standardized for age and sex according to the local laboratory reference values
 - d. Bone age x-ray ≥ 6 months less than chronological age
 - e. Diagnosis of at least one additional pituitary hormone deficiency
 - f. Congenital hypopituitarism due to congenital hypothalamic-pituitary defect (eg, ectopic posterior pituitary, pituitary hypoplasia, abnormal stalk, septo-optic dysplasia) or genetic defect (eg, GH1, POU1F1, or PROP1)
- 2) 6 months to 17 years old, inclusive, at Visit 1
 - a. If 3 to 17 years old, are taking daily hGH at a dose of ≥ 0.20 mg hGH/kg/week for at least 13 weeks but no more than 130 weeks prior to Visit 1
 - b. If ≥ 6 months but < 3 years old, are either hGH treatment-naïve or are taking daily hGH at a dose of ≥ 0.20 mg hGH/kg/week for no more than 130 weeks prior to Visit 1
- 3) Tanner stage < 5 at Visit 1
- 4) Open epiphyses (bone age ≤ 14.0 years for females or ≤ 16.0 years for males)
- 5) Written, signed, informed consent of the parent or legal guardian of the subject and written assent of the subject as required by the IRB/HREC/IEC

8.1.2 Exclusion Criteria

- 1) Weight of < 5.5 kg or > 80 kg at Visit 1
- 2) Females of child-bearing potential* (until non-clinical developmental toxicity studies have been completed and confirm participation by females of child-bearing potential to be acceptable)
*Although subjects who are of child-bearing potential at the time of enrollment will be exclusionary, subject who begin menses *during* the trial may continue.
- 3) History of malignant disease
- 4) Any clinically significant abnormality likely to affect growth or the ability to evaluate growth (eg, chronic diseases or conditions such as renal insufficiency, spinal cord irradiation, hypothyroidism, active celiac disease, malnutrition or psychosocial dwarfism)
- 5) Poorly-controlled diabetes mellitus (HbA1c $> 8.0\%$) or diabetic complications
- 6) Known neutralizing antibodies against hGH

- 7) Concomitant administration of other treatments that may have an effect on growth such as anabolic steroids or oral glucocorticoids, with the exception of hormone replacement therapies for hypopituitarism: hypothyroidism (thyroxine), adrenal insufficiency (hydrocortisone), hypogonadism (sex steroids), diabetes insipidus (desmopressin).
Note: Children with multiple hormonal deficiencies must be on replacement therapy for at least 13 weeks prior to Visit 1. If taking thyroid replacement therapy, child must be considered clinically euthyroid. If taking glucocorticoid replacement therapy, temporary adjustment, as appropriate, is acceptable.
- 8) Requiring inhaled glucocorticoid therapy (eg, asthma) at doses higher than those listed below for longer than 4 weeks during the 12 months prior to Visit 1.*
- Budesonide: 400 µg/d
 - Fluticasone: 264 µg/d
 - Beclomethasone: 504 µg/d
 - Flunisolide: 1000 µg/d
 - Mometasone: 211 µg/d
 - Ciclesonide: 264 µg/d
- *Although need for high-dose inhaled glucocorticoid therapy at the time of enrollment into this trial will be exclusionary, subjects who initiate high-dose inhaled glucocorticoid therapy for asthma *during* the trial may continue.
- 9) Concomitant administration of one of the following:
- Chronic oral glucocorticoids used for more than 3 months of the 12 months prior to Visit 1, other than as replacement therapy for congenital hypopituitarism
 - Weight-reducing drugs or appetite suppressants, unless used for management of ADHD
- 10) Major medical conditions, unless approved by Medical Monitor
- 11) Pregnancy
- 12) Presence of contraindications to hGH treatment
- 13) Known or suspected HIV-positive status
- 14) Known hypersensitivity to the components of the trial medication
- 15) Likely to be non-compliant with respect to trial conduct (in regards to the subject and/or the parent/legal guardian/caregiver)
- 16) Participation in any other trial of an investigational agent within 30 days prior to Visit 1
- 17) Prior exposure to investigational hGH
- 18) Any other reason that in the opinion of the investigator would prevent the subject from completing participation or following the trial schedule

8.2 Premature Subject Withdrawal

Early withdrawal occurs when an enrolled subject ceases participation in the trial, regardless of the circumstances, prior to the expected completion of the trial. Additionally, the investigator may discontinue the treatment of a subject at any time if considered to be in the subject's best interest. Unless informed consent is withdrawn, any subject who discontinues treatment should be encouraged to remain in the trial and attend all subsequent clinic visits. See [Section 7.3.1](#) for a list of stopping rules governing early termination of subjects from the trial.

In the case of premature discontinuation of a subject's participation in the trial (eg, withdrawal of informed consent), the investigator should schedule an Early Termination Visit to collect data, particularly AE follow-up data (if applicable), and to collect blood for laboratory evaluations. This visit should contain all assessments from Visit 3 (Week 26), and should be documented in the eCRF together with the reason(s) for trial discontinuation. In the case of treatment discontinuation for causes other than withdrawal of informed consent, subjects should be urged to remain in the trial and attend all subsequent trial visits. An Early Termination Visit is not required for subjects who remain in the trial after discontinuing study drug. However, if the subject is not willing to attend all subsequent trial visits, this should be considered a withdrawal from the trial and an Early Termination Visit should be scheduled.

Every effort should be made to observe subjects who have received at least 1 dose of study drug for the entire observation period, even if they discontinued trial treatment. The investigator should make every attempt to contact the subject/parent/legal guardian via phone to arrange the appropriate follow-up assessment(s) for such subjects.

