- *De novo* diagnosis of a slipped capital femoral epiphysis should result in a dose reduction or temporary discontinuation
- Identification of anti-hGH antibodies that are determined to be neutralizing

If treatment is discontinued, all subsequent visits and assessments should continue as planned. For additional details, refer to [Section 8.2](#).

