10.2.4 Early Termination Visits

Early Termination Visits are performed for any early termination/withdrawal of a subject from this clinical trial. Early Termination Visits are NOT to be performed for subjects who have terminated study drug but have continued to attend trial visits. The structure and assessments of the Early Termination Visit should be as similar as possible to the final visit (Visit 3).

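### Read literally, protocol 8.2 withdraws a child who is off study drug but would still attend Visit 3, against the protocol's own aim of observing every dosed child throughout

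*Protocol*

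**What the plan says.** Protocol 8.2 separates stopping drug from leaving the trial. A child who stops drug is to be urged to keep attending, and needs no Early Termination (ET) Visit while doing so. The exception is this: "However, if the subject is not willing to attend all subsequent trial visits, this should be considered a withdrawal from the trial". The rest of that sentence matters too: "this should be considered a withdrawal from the trial and an Early Termination Visit should be scheduled". The ET Visit repeats the full Visit 3 assessment set (8.2; Schedule of Events, note 2).

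Other passages on the same situation:

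- **Protocol 8.2, next paragraph:** "Every effort should be made to observe subjects who have received at least 1 dose of study drug for the entire observation period". This extends to children who have stopped treatment, and phone contact is to be used to arrange their follow-up.
- **Protocol 9.6.2:** "If treatment is discontinued, all subsequent visits and assessments should continue as planned".
- **Synopsis, Stopping/Dose Reductions:** equates the end of participation with withdrawn consent, and calls for the ET Visit then.
- **Protocol 7.1.2:** "all efforts will be made to keep missing data to a minimum".
- **Protocol 12.1.3:** new adverse events (AEs) are recorded up to Visit 3 or the ET Visit. Those ongoing at that point are followed until resolved or stable.
- **SAP 5.3, Table 2:** an ET visit is assigned to the scheduled visit with the nearest target day. The Visit 3 window opens on Day 138.
- **SAP 5.5:** the Full Analysis Set keeps every dosed child with any follow-up data.

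**The concern.** The exception is all or nothing. A family that has not withdrawn consent, and would bring the child to Visit 3 but not to an earlier visit, is classed with families that will not come at all.

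The primary objective is safety, and the safety endpoints are measured over the whole 26 weeks. Children who stop drug early may well differ from the others in tolerability, so follow-up cut short in this group may be informative. Children who terminate early are not expected to be replaced (protocol 8.3). SAP 5.2 gives imputation rules for covariates and dates but none for missing outcomes. Up to about 50 sites will apply the sentence as written.

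**Working it through.** **1. Who is caught.** From age 3, only Visits 2 and 3 follow the first dose. Children under 3 also have the C_max Visit.

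| Drug stopped | Family will attend | 8.2 read literally | If withdrawal meant no further visit |
|---|---|---|---|
| After Visit 2 | Visit 3 | Stays | Stays |
| After Visit 2 | None | Withdrawn | Withdrawn |
| Before Visit 2 | All remaining visits | Stays | Stays |
| Before Visit 2 | None | Withdrawn | Withdrawn |
| Before Visit 2 | Visit 3, but not an intermediate visit | **Withdrawn** | **Stays** |
| Before Visit 2 | An intermediate visit, but not Visit 3 | Withdrawn | Stays until that visit; no Week 26 observation either way |

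Only the fifth row costs a Week 26 observation that could have been had.

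**2. What that child still contributes.** A full Visit 3 assessment set at the ET Visit, follow-up of AEs ongoing then, and a place in the Full Analysis Set.

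**3. What is lost.**

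*New AEs.* Recording stops at the ET Visit. The protocol does not say when that visit takes place, so its timing here is an assumption. Share of a 26-week follow-up lost = (26 − ET week) / 26:

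- ET at Week 5: 21/26 = 81%
- ET at Week 9: 17/26 = 65%
- ET at Week 13: 13/26 = 50%

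*The Week 26 observation.* The target days in SAP Table 2 are 92 (Visit 2) and 183 (Visit 3). Their midpoint is (92 + 183)/2 = 137.5, which agrees with the Day 138 boundary. An ET visit up to Day 137 goes to an earlier window in the by-visit summaries, so the child has no Visit 3 value there. The data still appear in listings. An ET visit from Day 138 counts as Visit 3, and AE recording then ends at most 183 − 138 = 45 days before the target day.

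**4. How many children.** The documents give no discontinuation rate. For illustration only, assume that 3–8% of 150 stop drug, that half of these stop before Visit 2, and that a third to a half of those would skip an intermediate visit but attend Visit 3:

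- Low: 150 × 0.03 × 1/2 × 1/3 = 0.75
- High: 150 × 0.08 × 1/2 × 1/2 = 3

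That is roughly 1 to 3 children, on assumed rates.

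**5. The plan's sample-size figure.** The chance of seeing at least one AE of 2% incidence in 150 children is 1 − 0.98^150 = 0.9517, which reproduces the stated figure of at least 95%. The verdict explains why it does not measure this problem.

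**The case against.** The strongest reply is that 8.2, read as a whole, already favours retention. It uses advisory language and sets no deadline for the ET Visit, and its next paragraph covers every dosed child. Section 10.2.4 says "Early Termination Visits are NOT to be performed for subjects who have terminated study drug but have continued to attend trial visits" without requiring attendance at every visit. A sensible investigator need not expel a willing family. This limits the harm, but it leaves two instructions that point different ways. If the authors meant a family that will attend nothing further, the sentence should say so.

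A second reply is that the present rule has a merit. It secures a complete assessment close to exposure, while the family still cooperates. A promised Visit 3 may never happen, and then both assessments are lost. This stands, and the fix has to deal with it.

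A reader might infer more than the documents support:

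- *That the child's late safety data are lost outright.* They are not. The ET Visit, the follow-up of ongoing AEs and the analysis-set definition prevent that.
- *That participation ends at once.* No passage says so.
- *That 7.3.1 is contradicted because partial attendance is not among its reasons.* The list opens with "Valid reasons for which a subject's participation in the clinical trial may be discontinued include the following", so it is not exhaustive.
- *That the C_max Visit has no use once drug has stopped.* It also includes AE review, IGF-1 and hormone/glycemic tests (10.2.2.2).

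**Conclusion.** The inconsistency is real and the consequence small. Read literally, 8.2 withdraws a consenting child whom its own next paragraph, 9.6.2 and the synopsis would keep. The loss is confined to AEs that start after the ET Visit and, when that visit falls before Day 138, to the Week 26 observation. It arises only when drug is stopped before Visit 2, an intermediate visit is declined and Visit 3 would have been attended. The number of such children cannot be derived from the documents and is probably a few at most.

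It is tempting to add that losing two children takes the 2% AE probability from 95.17% to 1 − 0.98^148 = 94.97%, below the stated 95%. That does not follow. The calculation treats these children as contributing nothing, although they contribute AEs up to the ET Visit. The 150 is also approximate and describes ages 3 to 17, with the under-3s additional (protocol 8). The case rests on the conflicting text and the shortened AE capture. It is a worthwhile, cheap improvement and does not threaten the trial's conclusions.

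**What to change.** In 8.2, change the condition so that withdrawal applies to a child who will attend *no further* visit. Add that:

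- a child willing to attend Visit 3 stays in the trial, and declined visits are recorded as missed;
- the phone contact 8.2 already provides is also used to ask about new AEs;
- where the family agrees, the Visit 3 assessments are collected at an unscheduled visit around the time drug is stopped, without ending participation.

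The last item guards against a promised Visit 3 that does not happen. Section 10.2.3 limits unscheduled visits to focused assessments, so it needs a matching exception. SAP 5.3 already maps unscheduled visits by study day and needs no change.

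The cost is a few sentences in an amendment, tracking of missed visits, and one extra visit for a few children. The extra blood draw largely takes the place of a declined one, but should be checked against the volume limits in 11.10. A family that declines the extra visit and then misses Visit 3 would leave no off-drug assessment, and that risk remains. The change concerns data collection only and leaves the rules for stopping treatment untouched.

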8.3 Subject Replacement Criteria

Subjects who terminate early are not expected to be replaced.

9. TREATMENTS

9.1 Investigational Product

TransCon hGH will be provided as a lyophilized powder in single-use glass vials. The following materials for study drug reconstitution and administration will be provided to the investigational sites and distributed by the investigator to the subject/parent/legal guardian/caregiver:

- Prefilled syringes with 1 mL sWFI
- Syringes for administration
- Needles for reconstitution and administration

TransCon hGH will be dispensed to subjects/parents/legal guardians in sufficient amounts to provide the subject with enough study drug until the next dispensing visit.

9.2 Labeling

All study drug will be labeled according to GMP and local requirements. Subjects/parents/legal guardians will be provided with dosing and storage instructions. Study drug labels will comply with regulatory requirements of each country and will be printed in the local language.

9.3 Treatment Administered

TransCon hGH will be provided as a lyophilized powder in single-use glass vials to be reconstituted with 1 mL sWFI. Two concentrations will be available, the less concentrated for lighter weight subjects, the more concentrated for higher weight subjects:

- 12.1 mg hGH/vial (11.0 mg hGH/mL when reconstituted)
- 24.2 mg hGH/vial (22.0 mg hGH/mL when reconstituted)

Table 1 shows the weight ranges and corresponding drug concentration and volume to be administered to all subjects, regardless of weight, with an average dose of 0.24 ± 0.02 mg hGH/kg/week. If the concentration suggested in the preferred dosing column is unavailable, alternative dosing should be followed. It is imperative that investigators **do not** calculate a weight-based dose but rather follow the chart and administer the exact volume (based on weight) of the given concentration as indicated.

TransCon hGH will be injected SC into the left and right buttock, left and right thigh, and left and right abdomen by the subject/parent/legal guardian/caregiver except at Visit 1 where the trial staff may administer the first dose. To minimize local side effects, it is recommended to rotate the 6 injection sites in a subsequent manner (eg, right thigh, right abdomen, right buttock, left thigh, left abdomen, left buttock).

Table 1
TransCon hGH Bracketed Weight Table

Weight (kg)	DOSING		ALTERNATIVE DOSING ^a	
	Drug Concentration (reconstituted)	Volume (mL)	Drug Concentration (reconstituted)	Volume (mL)
5.5-6.6	11.0 mg/mL	0.13	22.0 mg/mL	Contact Medical Monitor
6.7-7.9	11.0 mg/mL	0.16	22.0 mg/mL	Contact Medical Monitor
8.0-9.5	11.0 mg/mL	0.19	22.0 mg/mL	Contact Medical Monitor
9.6-11.4	11.0 mg/mL	0.23	22.0 mg/mL	Contact Medical Monitor
11.5-13.9	11.0 mg/mL	0.27	22.0 mg/mL	Contact Medical Monitor
14.0-16.4	11.0 mg/mL	0.33	22.0 mg/mL	Contact Medical Monitor
16.5-19.9	11.0 mg/mL	0.39	22.0 mg/mL	Contact Medical Monitor
20.0-23.9	11.0 mg/mL	0.47	22.0 mg/mL	Contact Medical Monitor
24.0-28.9	22.0 mg/mL	0.29	11.0 mg/mL	0.57
29.0-34.9	22.0 mg/mL	0.35	11.0 mg/mL	0.69
35.0-41.9	22.0 mg/mL	0.41	11.0 mg/mL	0.83
42.0-50.9	22.0 mg/mL	0.50	11.0 mg/mL	0.50 + 0.50
51.0-60.5	22.0 mg/mL	0.60	11.0 mg/mL	0.60 + 0.61
60.6-73.4	22.0 mg/mL	0.73	11.0 mg/mL	0.73 + 0.73
73.5-87.7	22.0 mg/mL	0.88	11.0 mg/mL	0.88 + 0.88

^a To be used only when drug availability requires
kg = kilogram; mg = milligram; mL = milliliter

The reason for administering the exact volume as per Table 1 (rather than calculating the exact dose) is as follows. At the conclusion of this 26-week trial, if eligible, subjects may choose to enter the extension trial, CT-301EXT, during which TransCon hGH will initially be administered by syringe and needle. When the auto-injector, a unique device developed specifically for the administration of TransCon hGH, becomes available, subjects will be switched from the administration of TransCon hGH by syringe and needle to the auto-injector.

With the auto-injector, TransCon hGH will be provided in single-use dual chamber cartridges (DCCs). Multiple DCC presentations will be available containing 20% incremental increases in dose to support increasing weight ranges. Thus, each DCC will contain a specific quantity of TransCon hGH to support a specific weight range consistent with Table 1. The intention within this trial is to mimic dose increments that will eventually be administered via the auto-injector in the CT-301EXT (extension) Trial.

Additionally, dosing based on volumes for weight ranges with 20% bracketing assures that all subjects will receive an average of 0.24 mg/kg/week over the course of the trial.

Please refer to the Investigator's Brochure for complete details on the composition and characteristics of TransCon hGH.

